## Recruitment

Primary care clinicians: Once IRB approval has been received, we will discuss the study with primary care clinicians who have an established practice at 3 primary care practices and we will invite them to participate. If a primary care clinician would like to participate they will be asked to provide written informed consent. We will track the number of primary care clinicians who are invited to participate and the number who agree to participate.

Older adult primary care patients and their companions: Patients will be recruited to the study in a phased process. Patients who are scheduled for an upcoming visit with a participating primary care clinician will be identified from the clinic schedule via electronic scheduling software by our research team. Patients will be mailed a letter informing them of the study. The letter will state that patients will receive a call in about 10 days to explain the study in greater detail. The letter will include a postcard that patients may return by mail if they would like to “opt-out” from learning more about the study. Patients who do not “opt-out” will be called by phone to inquire about their interest in learning more about the study. We will attempt no more than six calls to potentially eligible participants – but will leave no more than two voice messages at their place of residence. Patients who at the time of the phone call express an interest in participating will be asked questions to determine eligibility. Companions of eligible patients will be contacted by research staff to introduce the study, answer questions, and state that participation is voluntary. Companions who express interest in participating will be asked questions to determine eligibility. For patients with significant cognitive impairment who are unable to interact with study staff by telephone, eligibility will be assessed by completing the screening survey with a knowledgeable informant.

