## **Participant Assignment**

Each patient-companion dyad will be randomized to treatment or control group in a 1:1 ratio using stratified, blocked randomization by doctor with alternating block sizes of 4 and 6 for each clinician. A statistical program, developed by the project statistician and unknown to study staff will be used to prospectively generate random treatment group assignment of study participants for each participating clinician. A set of opaque envelopes will be prepared for each clinician following the results of the statistical program. Upon providing informed consent, research staff will open the next sequentially ordered envelope specifying treatment group by clinician. Patient-companion dyads assigned to

the treatment group will receive a copy of the pre-visit checklist and a clipboard and pen. Patient-companion dyads assigned to the control group will receive care as usual. Participants and research staff responsible for the randomization protocol at the enrollment visit will be aware of participant assignment status after it occurs. The PI, project statistician, and research staff responsible for coding study outcomes will be blinded throughout the study. As randomization occurs at the level of the patient-family dyad, clinicians will care for patients in both groups. Clinicians will be blinded to group assignment.

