## Analysis

Analyses will be performed in SAS statistical software, with each patient-companion dyad and their recorded visit as the unit of analysis. In this two-group randomized pilot trial, we will compare the effects of the refined checklist on medical communication among up to 100 (50 per group) patients ages 65+ with cognitive impairment and their companion. Simple statistics (frequency distributions, group means) will be used to assess potential differences between eligible patients willing and unwilling to participate, between enrolled participants assigned to intervention and control groups, and process measures relating to completion of the agenda setting intervention. We will rely on established cut-points and approaches to constructing primary and secondary outcome measures, as well as measures of patient and companion attributes that will serve as control variables (socio-demographic characteristics, health status, aspects of the patient and companion relationship). We will rely on established cut-points of the Mini-Mental State Examination test to categorize patient participants as having mild (scores of 20-25), moderate (scores of 10-20) or severe (scores of less than 10) cognitive impairment.(41, 42) We will primarily evaluate the consistency, direction, and magnitude of differences in study outcomes by undertaking analyses that are stratified by intervention group (checklist versus usual care) and for the subgroups of patient cognitive function (mild, moderate, or severe, based on the Mini-Mental State Examination cut-points). Intervention effects on primary and secondary outcomes will be examined using regression models in which the main independent variable is treatment assignment. We will use generalized estimating equations (PROC GENMOD in SAS, version 9.4 (SAS Institute, Cary North Carolina)) to assess the direction, magnitude, and statistical significance of between-group differences in outcomes. The generalized estimating equations method will be used because it accounts for within-clinician clustering of patients and the different numbers of enrolled patient-companion dyads per clinician.(46) An exchangeable correlation structure will be assumed. Regression models will include treatment assignment (agenda setting versus usual care) and patient-level covariates that are postulated as affecting communication, such as age, gender, and cognitive function. We will evaluate recruitment, retention, and the timeliness and completeness of collected data,(47) as well as checklist acceptability (utility, burden, helpfulness) using questions from our formative work. (33) The statistical significance of patient-companion concordance/discordance on priorities for the visit agenda will be assessed with McNemar's test. We recognize the need for caution in interpreting pilot trial results. We will evaluate recruitment and dropout rate as well as effect size of primary and secondary outcomes to help inform the design and sample size calculations for a larger trial. We will examine similarities and differences in pilot trial results and our initial proof-of-concept study. The ultimate goal of the Aim 2 pilot trial is to demonstrate the feasibility of implementing the study protocol among primary care patients with a range of cognitive impairment and their companion and to glean insight regarding effects of the refined checklist for medical communication.

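### The clinician-clustered GEE tests name no variance estimator or small-sample correction; an uncorrected sandwich test over-rejects if clinicians are few

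*Combined protocol and SAP*

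**What the plan says.** The Analysis section names the method and software ("We will use generalized estimating equations (PROC GENMOD in SAS, version 9.4") and the purpose: "to assess the direction, magnitude, and statistical significance of between-group differences in outcomes". On the choice of method it states: "The generalized estimating equations method will be used because it accounts for within-clinician clustering of patients"; it also cites the unequal numbers of dyads per clinician. On the working correlation: "An exchangeable correlation structure will be assumed". The models contain treatment plus patient-level covariates, with age, gender and cognitive function given as examples.

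The plan does not say whether standard errors are empirical (sandwich) or model-based, which test statistic and reference distribution apply, whether a small-sample correction is made, or what significance level is used.

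The clusters are clinicians, not the 3 practices. Their number is not given. The Recruitment section says only: "We will track the number of primary care clinicians who are invited to participate and the number who agree to participate". Participant Assignment randomises dyads within clinician, "using stratified, blocked randomization by doctor with alternating block sizes of 4 and 6 for each clinician". Study Design caps the trial at 100 dyads, 50 per group.

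**The concern.** The sandwich variance is justified as the number of clusters grows. With few clusters it is biased downward and is itself noisy, so comparing the Wald statistic with a normal distribution gives p-values that are too small and intervals that are too narrow. With at most 100 dyads and blocks of 4 and 6 for each clinician, the number of clinicians is probably modest, although nothing in the plan bounds it.

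The plan therefore picks a method whose validity depends on the cluster count, without giving that count or a safeguard. It applies the method to the primary outcome, the patient-centred communication ratio, and to the secondary outcomes. Randomising within clinician does not remove the problem, because the bias lies in the variance estimator and not in the treatment contrast.

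**Working it through.** The plan states no error rate, so there is no figure to reproduce. The check simulates trials with no true effect.

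**Inputs from the plan:** 100 dyads, 1:1 (Study Design); allocation within clinician in blocks of 4 and 6 (Participant Assignment); exchangeable GEE clustered by clinician, with three covariates matching the examples given (Analysis).

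**Assumptions, because the plan gives no value:** two-sided 5% level; K = 5 to 40 clinicians; ICC 0.05 or 0.15; equal or unequal numbers of dyads per clinician; normal or lognormal outcome (the primary outcome is a ratio); identity link.

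**Formulas.** For clinician i with design matrix X_i, working covariance V_i and residuals r_i, let A = Σ X_i′V_i⁻¹X_i.
- Model-based variance: A⁻¹.
- Sandwich variance: A⁻¹ [Σ X_i′V_i⁻¹ r_i r_i′ V_i⁻¹X_i] A⁻¹.
- Mancl-DeRouen variance: the same, with r_i replaced by (I − H_i)⁻¹ r_i, where H_i = X_i A⁻¹ X_i′V_i⁻¹.
- The test statistic is estimate / SE, compared with 1.96, or with the t quantile on K − 2 df for the corrected version.

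**Results.** Each setting has 3,000 null trials, so the Monte Carlo SE at 5% is √(0.05 × 0.95 / 3000) = 0.4 points. Ranges run over the assumed settings.

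| Clinicians | Mean dyads each | Sandwich SE / true SD | Sandwich z rejects | Mancl-DeRouen, t(K−2) rejects |
|---|---|---|---|---|
| 5 | 20 | 0.763-0.837 | 14.8-21.1% | 1.6-2.7% |
| 10 | 10 | 0.867-0.912 | 9.5-11.8% | 3.0-4.4% |
| 15 | 6.7 | 0.871-0.933 | 8.3-11.2% | 3.6-5.5% |
| 20 | 5 | 0.904-0.935 | 7.2-9.6% | 3.9-5.2% |
| 30 | 3.3 | 0.932-0.952 | 7.0-7.5% | 3.8-5.0% |
| 40 | 2.5 | 0.928-0.962 | 6.3-8.1% | 3.7-5.3% |

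The model-based z test rejected 4.4-6.6% over all K.

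**Hand check.** If the SE were a constant fraction f of the truth, rejection would be 2[1 − Φ(1.96f)]. At K = 10 (f = 0.867 to 0.912) this gives 8.9% to 7.4%; at K = 20 (f = 0.904 to 0.935), 7.6% to 6.7%. The simulated rates are somewhat higher, as expected when the SE also varies from trial to trial.

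**Second simulation.** Separately written code, with 0 or 3 covariates, gave sandwich-z rates of 9.4-12.3% at 10 clinicians, 7.0-9.8% at 20, 5.9-8.0% at 30 and 6.1-7.0% at 40. With 7 covariates the rates were 11.3-13.4% at 10 and 9.0-9.8% at 20. The ICC made almost no difference; cluster count, unequal panels and number of covariates drive the result.

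**If the checklist effect varies between clinicians.** The assumptions are effect variance 0.05 / 0.10 on a unit-variance normal outcome, ICC 0.10 and unequal clusters, with 2,000 trials per setting (Monte Carlo SE 0.5 points).

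| Clinicians | Model-based z | Sandwich z | Mancl-DeRouen, t(K−2) |
|---|---|---|---|
| 5 | 9.0 / 13.4% | 18.5 / 21.1% | 2.5 / 3.2% |
| 10 | 7.9 / 9.6% | 13.1 / 13.4% | 4.6 / 5.1% |
| 20 | 6.4 / 7.2% | 8.6 / 9.5% | 4.1 / 4.4% |
| 30 | 6.0 / 7.0% | 7.1 / 8.6% | 4.2 / 5.5% |

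**The case against.** The strongest reply is that the defect depends on two facts the plan does not give: how many clinicians take part, and which standard error or test is used. Other tests fit the same text and are close to nominal. The model-based z test is one. A robust score test is another, at 3.8-5.4% with 10 clinicians and 5.0-5.8% with 20 when the working correlation is fixed at its true value. The case against the model-based test needs an effect that varies by clinician, for which the documents give no value. Finally, this is a feasibility pilot that puts direction and magnitude first and asks for care in reading its results, with no decision rule tied to a p-value.

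Much of this stands as a limit on the claim. The sandwich default is an inference from the named procedure, not plan text, and it cannot be said that this trial's p-values will be wrong by a given amount. The pilot purpose also limits the harm.

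It does not remove the point. The plan sets out to assess "magnitude, and statistical significance of between-group differences in outcomes", and the same data could give materially different p-values depending on an unstated choice. At the inferred default, rejection exceeded 5% at every cluster count tested, including 30-40. General caution in interpretation does not correct an anti-conservative test.

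**Conclusion.** The concern holds, conditionally on the uncorrected sandwich standard error being used with a normal reference. The size of the inflation is set by a number the plan omits: roughly two to two and a half times the assumed 5% level at 10 clinicians, and only 1 to 3 points above it at 30-40. Effect estimates are not touched; significance statements and interval widths are. The omission itself is certain from the text. The rates rest on the assumed level, ICC, outcome shapes and cluster sizes listed above. This should be fixed before analysis, but it does not threaten the pilot's feasibility aim.

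**What to change.** Keep the GEE point estimate and add one or two sentences to the Analysis section:
- State the variance estimator. Base confidence intervals and p-values on a bias-corrected sandwich variance, for example Mancl-DeRouen, with a t reference on (number of clinicians − 2) df.
- State the significance level and the expected number of clinicians, and report the actual number with each result.

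Other corrections are acceptable if named in advance. A clinician random-intercept model with Kenward-Roger df, or the exchangeable model-based standard error, would also serve. Both rely on a checklist effect that does not vary by clinician, and the plan should say so if it chooses one.

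No new data are needed. If the named procedure does not offer the correction, another routine in the same package is required. The price is wider intervals: on average 1.10-1.14 times the default width at 30-40 clinicians, 1.17-1.20 at 20, 1.35-1.43 at 10 and 2.1-2.3 at 5. Part of this is the t multiplier alone (2.306 / 1.96 = 1.18 at 10 clinicians; 3.182 / 1.96 = 1.62 at 5). At 5 clinicians the correction is conservative, and the report should say so if the trial ends there.

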## Study Design

We will conduct a two group pilot randomized trial of up to 100 (50 per group) patients ages 65+ with cognitive impairment and their unpaid companion to test the effects of the refined checklist for medical communication. Each patient-companion dyad will be randomized to the intervention (to receive the checklist) or to a control protocol. Aim 2 has been designed as a pilot trial to evaluate the feasibility of delivering the study protocol to patients with cognitive impairment and their companions in primary care, and to generate preliminary evidence regarding the effect of the checklist on medical communication. For these reasons, the control group protocol will comprise usual care which is in this case existing clinical practice.(35, 36) Patients (when feasible), companions, and doctors in both intervention and control groups will complete in-person post-visit surveys immediately after the visit. Patients (when feasible) and companions will separately complete follow-up surveys by telephone two weeks after the doctor visit conducted by a research staff member. Because of high (100%) retention in our proof-of-concept study, we expect low dropout.

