## Participants

We propose to enroll as many as 100 patient-companion dyads to provide us with information about the feasibility and acceptability of our study protocol, and preliminary insight regarding the effects of the intervention on medical

communication. We estimate that we will screen as many as 2,000 patients ages 65 and older to reach our target enrollment. In our proof of concept study 263 patients were screened and 32 (12.1%) patient-companion dyads were enrolled. As the Aim 2 pilot study will impose eligibility criteria pertaining to cognitive impairment, we have conservatively estimated that we will need to screen a larger number of older patients to attain recruitment goals than in our proof-of-concept study. However, we note that prevalence of mild cognitive impairment is not uncommon, and may be as high as 42% among older adults (37). The sample size of this study is based on practical factors related to available funding and duration of the R21 mechanism that is supporting this project.

Participants of this study will include three groups: (1) Older adult primary care patients with cognitive impairment, (2) Companions of older adult primary care patient study participants, and (3) primary care clinicians.

Inclusion/exclusion criteria for each of these groups are as follows:

- A. Older adult primary care patients. Inclusion criteria: 65 years or older, established patient of participating primary care clinician, regularly attend medical visits with one or more family member or unpaid friend “companion(s)”, agree to allow companion to be contacted and participate in the study, authorize disclosure of PHI in their electronic health record, able to provide informed consent or have a legally authorized representative. Exclusion criteria: younger than 65 years, no evidence of cognitive impairment, do not attend medical visits with family member or unpaid friend.
- B. Family companion. Inclusion criteria: Family member (spouse, adult child, parent, adult sibling) or unpaid friend who accompanies older adult participant to medical visits. Exclusion criteria: paid non-family member who accompanies patient to visits.
- C. Primary care clinicians. Inclusion criteria: practicing physician, nurse practitioner or physician assistant at a participating primary care practice.

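### Dyads are randomised within clinician, but the clinician-clustered GEE has no stated standard error; the usual sandwich version would give intervals that are too narrow with few clinicians

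*Combined protocol and SAP*

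**What the plan says.** Participant Assignment allocates dyads 1:1 "using stratified, blocked randomization by doctor with alternating block sizes of 4 and 6 for each clinician". It adds: "As randomization occurs at the level of the patient-family dyad, clinicians will care for patients in both groups". Clinician is therefore a randomisation stratum, and both arms are meant to occur within each one.

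The Analysis section works "with each patient-companion dyad and their recorded visit as the unit of analysis". It fits generalized estimating equations in PROC GENMOD, on the ground that the method "accounts for within-clinician clustering of patients" and copes with unequal numbers of dyads per clinician. On the model itself it says: "An exchangeable correlation structure will be assumed. Regression models will include treatment assignment (agenda setting versus usual care) and patient-level covariates". The covariates it gives as examples are age, gender and cognitive function; no clinician term is listed.

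The section does not say whether standard errors are empirical (sandwich) or model-based. It gives no small-sample correction and no reference distribution. Recruitment and Consent Process mention 3 practices, but no section gives a number of clinicians. Study Design describes a "two group pilot randomized trial of up to 100 (50 per group) patients ages 65" and over. Participants explains the size: "The sample size of this study is based on practical factors related to available funding and duration of the R21 mechanism".

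**The concern.** A GEE is usually reported with the empirical variance, which is built from one residual sum per cluster. Here the clusters are clinicians, so that variance is estimated from as many independent pieces as there are clinicians, whatever the number of dyads. With few clusters it tends to be too small, and a normal reference adds to the error.

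The design does not need this. Both arms occur within clinician, so differences between clinicians largely cancel from the treatment contrast, and its precision can be estimated from variation among dyads.

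What is at stake is the interval and p-value for the checklist effect. The plan intends to judge significance from this model and to carry the effect size into the design of a larger trial. An interval that is too narrow would make the pilot look more informative than it is.

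**Working it through.** **Inputs from the documents.** N = 100 dyads (the maximum), 1:1 allocation, clinician as stratum, alternating blocks of 4 and 6, exchangeable GEE clustered on clinician. The plan gives no power, alpha, SD, ICC or number of clinicians, so it has no figure of its own to reproduce.

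**Assumptions.** K = 6, 10, 15 or 25 clinicians with unequal loads, ICC 0.10, normal outcome with SD 1, the same effect for every clinician, two-sided 5% test.

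**Step 1: precision of the contrast.** With balance within clinician, SE ≈ √[4(1 − ICC)/N] = √(4 × 0.90/100) = 0.190 SD. K does not enter. At K = 10 the simulated SD of the estimate is 0.191 for the GEE and 0.193 with clinician fixed effects. The GEE point estimate therefore already uses all the dyads.

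**Step 2: why the sandwich test misbehaves.** Treat the sandwich statistic as roughly t with K − 1 degrees of freedom. Comparing it with 1.96 then gives P(|t| > 1.96) = 10.7 / 8.2 / 7.0 / 6.2% for K = 6 / 10 / 15 / 25. The downward bias of the sandwich with few clusters adds the rest.

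**Step 3: simulation** (1,000 to 2,500 trials per cell).

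| Analysis | Result | K = 6 | 10 | 15 | 25 |
|---|---|---|---|---|---|
| GEE, uncorrected sandwich, normal reference | Type I error | 15% | 11% | 10% | 7% |
| Clinician as stratum, dyad-level error | Type I error | 5% | 6% | 5% | 5% |
| | 95% CI half-width (SD) | 0.38 | 0.38 | 0.38 | 0.40 |
| | Power at 0.5 SD | 75% | 74% | 73% | 70% |
| GEE, model-based SE | Type I error | 4.7% | 5.7% | 5.7% | 5.8% |
| | 95% CI half-width (SD) | 0.37 | 0.37 | 0.38 | 0.38 |
| | Power at 0.5 SD | 75% | 75% | 75% | 73% |
| GEE, bias-corrected sandwich (Mancl-DeRouen), t(K − 1) | Type I error | 4–5% | 4–5% | 4–5% | 4–5% |
| | 95% CI half-width (SD) | 0.52 | 0.45 | 0.42 | 0.40 |
| | Power at 0.5 SD | 50% | 59% | 65% | 69% |

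With 1,000 trials the simulation error at 5% is √(0.05 × 0.95/1000) = 0.7 percentage points, so 5 to 6% cannot be told apart from nominal.

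**Step 4: check of the widths at K = 6.** Stratum analysis: t(93) × 0.190 = 1.986 × 0.190 = 0.377, as simulated. Corrected sandwich: t(5) × 0.190 = 2.571 × 0.190 = 0.488 before the bias correction, against 0.52 simulated. The stratum interval is 1 − 0.38/0.52 = 27% narrower at 6 clinicians, 1 − 0.38/0.45 = 16% narrower at 10, and no narrower at 25 (0.40 against 0.40).

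**Step 5: other settings.** With three patient covariates and ICC from 0.05 to 0.20, the uncorrected sandwich gives 28–31% at 3 clinicians, 15–16% at 6, 11–12% at 10 and 7–8% at 30. Clinician fixed effects stay between 4.1 and 5.9% throughout. A right-skewed (log-normal) outcome, plausible for a ratio, gave the same pattern.

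**Step 6: effect varying between clinicians.** With an assumed SD of 0.2 for that variation, the stratum analysis rejects a zero average effect 8 / 7 / 6 / 6% of the time, against 16% and 12% for the uncorrected sandwich at 6 and 10 clinicians. With a variance of 0.10 (SD √0.10 = 0.32), the stratum analysis gives 11 / 10 / 8 / 7%, the model-based GEE 11 / 9 / 8 / 8%, and the corrected sandwich stays at 4–5%.

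**The case against.** A reader might infer that clinician has been left out, so that the whole analysis rests on the number of clinicians and not on the dyads. The documents do not support that. Clinician enters through the exchangeable working correlation, treatment varies within clinician, and Step 1 shows that the estimate draws on every dyad. Nor is the missing clinician term the cause: the planned GEE, without that term but with model-based standard errors, holds about 5 to 6%. The fault lies in the sandwich variance with few clusters, and the plan does not say that it will use that variance.

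It is also tempting to say that any GEE interval here must be either too narrow or needlessly wide. That is wrong for the same reason, since the model-based version is neither.

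The target of inference is a fair point too. The stratum and model-based analyses speak to the participating clinicians. If the effect differs between clinicians and the aim is to generalise beyond them, the wider corrected sandwich has a proper role, and the plan does look ahead to a larger trial.

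Finally, this is a pilot sized by funding, with feasibility as its main goal, and its authors ask for caution in reading the results. That limits the consequences. It does not settle which standard error will be reported, and caution does not repair an interval carried into later planning.

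**Conclusion.** The point holds in conditional form. The plan leaves open the one choice, the standard error, on which the validity of the test depends. Under the usual choice the type I error would be about 15 / 11 / 10 / 7% for 6 / 10 / 15 / 25 clinicians instead of 5%. Only the intervals and p-values are affected, not the estimate.

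These figures rest on an assumed number of clinicians, ICC 0.10, 100 dyads, a normal outcome and a common effect. The documents fix none of these except the maximum of 100 dyads, so the actual size cannot be determined from them. Binary outcomes such as discussion of memory were not simulated. For a pilot this is a worthwhile and cheap improvement rather than a fatal defect.

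**What to change.** In the Analysis section:

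- State that the treatment effect on continuous outcomes is estimated with clinician as a stratum (CLASS) term and dyad-level residual error. Keeping the exchangeable GEE with model-based standard errors is an equivalent alternative; name one of the two in advance. Adding a clinician term while retaining the clinician-level sandwich would not be enough, because the weakness is in that variance.
- Report the number of clinicians and the number of dyads per clinician and arm.
- Give the exchangeable GEE with a small-sample-corrected sandwich and a t reference as a sensitivity analysis, with the within-clinician correlation.
- State the standard error for binary outcomes as well.

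The cost is a few sentences and no new data. There are three small downsides. Inference is to the participating clinicians, and a clinician whose dyads all fall in one arm adds nothing to a stratum analysis. If the effect varies between clinicians (assumed SD 0.2), the type I error for an average effect rises to about 7–8% with 6 to 10 clinicians. The gain in precision over the corrected GEE is gone at about 25 clinicians.
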